3.2. Treatment Discontinuation

Patients were informed that they have the right to withdraw from the study at any time for any reason without prejudice to their medical care.

A patient may be discontinued from treatment for any of the following reasons:

- Patient's request
- Patient's unwillingness or inability to comply with the protocol
- Pregnancy
- Use of prohibited medication (e.g., hydroxyurea)
- Medical reason or adverse event, at the discretion of the investigator and/or the medical monitor
- Hypersensitivity reaction to study drug
- At the discretion of the sponsor (e.g., termination of the study or a dose level)

A patient may be withdrawn from the study for any of the following reasons:

- Patient's request
- Patient's unwillingness or inability to comply with the protocol
- Death
- Loss to follow-up
- At the discretion of the sponsor (e.g., termination of the study)

Patients who discontinued treatment early completed the end of treatment (EOT) follow-up visit at the time of discontinuation and then completed the end of study (EOS) follow-up visit approximately 28 days later.

3.3. Rollover to Extension Study

Consenting patients that meet the A536-06 eligibility criteria may immediately roll over from A536-04 to study A536-06 following the last ACE-536 dose. These patients may forego the End of Study (EOS) visit in study A536-04 to begin study A536-06.

Patients who complete the EOS visit for study A536-04 and are \geq 28 days post EOS visit may also roll over to study A536-06. These patients will be re-assessed for eligibility by meeting all eligibility criteria plus additional inclusion criteria for study A536-06.

Patients who do not meet the above criteria (e.g., $>$ 35 days after last dose in study A536-04 and $<$ 28 days post EOS visit in study A536-04) may still participate, but should not begin study A536-06 C1D1 until they have reached \geq 28 days post EOS visit from study A536-04.

3.4. Sample Size

There was no formal sample size calculation for the dose escalation portion of the study. A sample size of 30 evaluable patients in the expansion cohort will provide approximately 87% power with 1-sided significance level of 0.05 to differentiate an erythroid response rate of 30% from a minimal erythroid response rate of 10%.

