15.2.2. Primary Efficacy Analysis

The primary efficacy endpoint is defined as the proportion of β -thalassemia patients who have an erythroid response, defined as 1) a hemoglobin increase of \geq 1.5 g/dL from baseline for \geq 14 days (in the absence of RBC transfusions) in non-transfusion dependent patients or 2) \geq 20% reduction in RBC transfusion burden compared to pretreatment in transfusion dependent patients.

Transfusion burden will be defined as the ratio of RBC transfusion units (or mLs) transfused during an interval to the duration (days) of that interval, where the interval may be during the pretreatment period or the treatment plus follow-up period. The interval during the pretreatment period will be defined as the 12 weeks prior to Cycle 1 Day 1. An interval during the treatment plus follow-up period will be defined as any 12-week interval after Cycle 1 Day 1.

The erythroid response will be summarized using both a point estimate and its exact 95% confidence interval based on binomial distribution. The primary efficacy analysis will be performed using the EE population.

No direct comparison testing with concurrent or historical controls will be performed.

Baseline hemoglobin will be an average of 2 or more measurements; one measure performed within one day prior to Cycle 1 Day 1 and at least one other performed during the screening period (Day -28 to Day -1). Hemoglobin measurements within 2 weeks following RBC transfusion will be excluded.

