5.2. General Considerations

Unless otherwise noted, continuous data will be summarized with the following descriptive statistics: number of observations (n), mean, standard deviation (STD), minimum, median, and maximum. Categorical data will be summarized with frequencies (n) and percentages (%). In cases where missing data cause percentages not to sum to 100, a missing data row will be

provided. Percentages will use column totals as the denominator unless otherwise indicated. For time to event variables, the Kaplan-Meir curves will be presented if the number of patients is more than 5.

All study data will be included in study data listings. Missing data will generally be treated as missing, not imputed, unless otherwise stated.

All summaries will be presented by dose cohort, and may also be presented by low/high dose groups as specified. The summaries may also be presented for TD and NTD patients separately as specified. All summaries will be descriptive. No formal hypothesis testing is planned.

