5.7.1. Primary Efficacy Endpoint

The primary efficacy endpoint is the proportion of β -thalassemia patients who have an erythroid response, defined as below:

- For non-transfusion dependent (NTD) patients, a hemoglobin increase of ≥ 1.5 g/dL from baseline sustained for ≥ 14 days (in the absence of RBC transfusions). Hemoglobin measurements within 14 days following RBC transfusion or after 56 days of last dose will be excluded from analysis.
- For transfusion dependent (TD) patients, a $\geq 20\%$ reduction in RBC transfusion burden during any rolling 12-week window on treatment compared to baseline. The rolling 12-week window starts on Day 1 and increments by 1 day, e.g., from day 1 to day 84, day 2 to day 85, day 3 to day 86, etc. The search window ends on last dose day + 56 days or last day of hemoglobin measurement, whichever is earlier.

A point estimate of the proportion of patients having a response will be presented along with its associated exact 95% confidence interval based on binomial distribution for NTD and TD patients separately.

The complete hemoglobin measurements and RBC transfusion records will be listed for each patient.

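### The 87% power figure is a normal approximation: the exact one-sided test on 30 patients gives 84%, and the two-sided exact intervals actually reported exclude 10% less often still

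*SAP*

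**What the plan says.** Protocol 15.3 and SAP 3.4 carry the same sentence, and the synopsis repeats it: "A sample size of 30 evaluable patients in the expansion cohort will provide approximately 87% power with 1-sided significance level of 0.05". The rates to be separated are 30% and a minimal 10%. No test or formula is named for the power.

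On the analysis, Protocol 15.2.2 says: "The erythroid response will be summarized using both a point estimate and its exact 95% confidence interval based on binomial distribution". It does not split the estimate by transfusion status and uses the Efficacy Evaluable population. SAP 5.7.1 does split it, giving the "exact 95% confidence interval based on binomial distribution for NTD and TD patients separately". SAP 5.7 adds presentation by dose cohort and by low and high dose group. SAP 4.1 assigns all efficacy analyses to the ITT population, and SAP 5.13 records that the Efficacy Evaluable population was removed. SAP 5.2 states: "No formal hypothesis testing is planned".

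**The concern.** The sizing statement and the reported analysis differ in three ways.

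- **Method.** The power figure comes from an approximation. With 30 patients and a null rate of 10%, only 3 responders are expected under the null, so the approximation and the exact distribution can part company.
- **Level.** The sizing uses a one-sided 0.05 level. The lower limit of a two-sided 95% interval works at one-sided 0.025.
- **Denominator.** The sizing treats the 30 patients as one group. SAP 5.7.1 reports two smaller groups and lists no pooled expansion-cohort estimate.

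At stake is how the result will be read. Someone who sees 87% power in the plan and then an interval that includes 10% may take this as evidence against a 30% response rate, when such an interval is a common outcome even if the true rate is 30%.

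**Working it through.** **Inputs.** n = 30, null rate 0.10, alternative 0.30, one-sided level 0.05 (Protocol 15.3, SAP 3.4). Two-sided exact 95% binomial interval (Protocol 15.2.2, SAP 5.7.1). At least 12 NTD and at least 12 TD patients among the 30 (SAP 3.1), so each group has between 12 and 30 − 12 = 18.

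**Step 1: reproduce the stated figure.** Use the null variance for the critical value, the alternative variance for power, and a continuity correction of 1/(2n):

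- Null standard error: √(0.10 × 0.90 / 30) = 0.0548
- Alternative standard error: √(0.30 × 0.70 / 30) = 0.0837
- Power = Φ[(0.20 − 1.645 × 0.0548 − 0.0167) / 0.0837] = Φ(1.114) = 0.867

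This is the plan's 87%. Without the continuity correction the result is 90.6%; the arcsine method gives 88.1%. The uncorrected formula at two-sided 0.05 also gives 86.6%, but that is not the stated sidedness.

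**Step 2: exact one-sided test, n = 30.** For X responders, size is P(X ≥ r | 0.10) and power is P(X ≥ r | 0.30).

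| Cut-off r | Size | Power |
|---|---|---|
| 6 | 7.3% | 92.3% |
| 7 | 2.6% | 84.0% |
| 8 | 0.8% | 71.9% |

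The smallest cut-off with size at or below 5% is 7, so exact power is 84.0%. No attainable cut-off gives 87% within the 5% level.

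**Step 3: two-sided exact 95% interval on all 30 patients.** The Clopper-Pearson lower limit is the 2.5% quantile of a Beta(x, n − x + 1) distribution.

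- 7/30: lower limit 9.93%, so 10% is not excluded
- 8/30: lower limit 12.28%, so 10% is excluded

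At a true rate of 30%, P(X ≥ 8) = 71.9%. For comparison, the exact one-sided 95% lower limit at 7/30 is 11.5%, in line with the cut-off in Step 2.

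**Step 4: the same interval within NTD or TD, expansion cohort.**

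| Patients in group | Fewest responders that exclude 10% | Probability at a true 30% |
|---|---|---|
| 12 | 5 | 27.6% |
| 15 | 5 | 48.5% |
| 17 | 5 | 61.1% |
| 18 | 6 | 46.6% |

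The probability rises with group size up to 17 and drops at 18, where the required count goes from 5 to 6. The range over 12 to 18 is therefore about 28% to 61%.

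**The case against.** The power statement says approximately, names no method, and follows from its own inputs by a standard formula. The word exact is attached to the confidence interval, not to the sizing. A reader might infer that 87% is a calculation error. The documents do not support that, since Step 1 recovers it. This part of the objection stands.

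A reader might also infer that the trial would contradict itself at 7/30, with the sizing rule declaring success while the interval does not. Neither document contains a 7/30 rule, a success criterion or any decision tied to excluding 10%. SAP 5.2 rules out formal testing, and Protocol 15.2.2 rules out direct comparison testing with concurrent or historical controls. No conclusion of the trial changes between 84% and 87%.

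Nor is 72% the figure for the interval that SAP 5.7.1 reports. It belongs to a single interval on all 30 patients, which fits the unsplit wording of Protocol 15.2.2. The SAP's display is by NTD and TD, where the probability is lower.

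The reference to evaluable patients is not a hidden change of population: SAP 5.13 discloses and explains the removal, so the word in SAP 3.4 is a leftover. Finally, SAP 3.1 describes enrolment in the past tense, so restating the power cannot alter the sample size.

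What the objection leaves untouched is that the only quantitative justification for the cohort describes a one-sided, pooled, approximate calculation, while the reported results are two-sided, split and exact.

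**Conclusion.** The point holds as a mismatch between sizing and reporting, of minor to moderate weight. By the exact one-sided 0.05 test the power is 84.0%, about 3 points below the stated figure; one more patient would nearly close that gap (86.5% at n = 31). The larger difference is with the reported intervals: 71.9% for a two-sided 95% interval on all 30 patients, and about 28% to 61% within NTD or TD.

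These figures assume a true response rate of 30%, in each group as well as overall. They also assume that all 30 expansion patients are analysed and that the enrolment minimum of 12 per group carries over to the SAP's programmed definition of transfusion dependence. The NTD and TD range applies to the expansion-cohort display. The combined high-dose group would have larger denominators, but the documents do not give its NTD and TD counts.

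**What to change.** 1. In SAP 3.4, state that 30 patients in the pooled expansion cohort give 84% power by the exact one-sided 0.05 test (at least 7 of 30 responders) for 30% against 10%. Replace the reference to evaluable patients with the ITT population.
2. Make the same restatement of the power in Protocol 15.3 and the synopsis. If the protocol is no longer being amended, record the difference in SAP 5.13.
3. In SAP 5.7.1, add the pooled expansion-cohort response rate with its exact 95% interval beside the NTD and TD results, so that the quantity the cohort was sized for is reported.
4. State that, at a true rate of 30%, the two-sided 95% interval excludes 10% with 72% probability pooled and about 28% to 61% within NTD or TD.
5. Optionally, show the exact one-sided 95% lower limit beside the pooled interval as a descriptive figure, with no formal test.

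The cost is a slightly less favourable stated power, one extra summary line and some wording. Nothing changes in design, data collection or sample size.

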4. ANALYSIS POPULATIONS

For all analysis populations, patients will be analyzed according to assigned cohort.

4.1. Intent-to-Treat (ITT) Population

The intent-to-treat (ITT) population will consist of all enrolled patients. This population will be used for all efficacy analysis.

4.2. Safety Population

Safety population will include all patients who received at least 1 dose of ACE-536. This population will be used for all safety analysis.

4.3. Pharmacokinetics (PK) Population

Pharmacokinetics population will include all patients who have received at least 1 dose of ACE-536 and have sufficient pharmacokinetic samples collected and assayed for PK analysis

5. STATISTICAL METHODOLOGY

5.1. Definitions

Transfusion Dependent (TD)

Based on protocol, TD patients are defined as those who required ≥ 4 units of RBCs every 8 weeks (confirmed over 6 months prior to Cycle 1 Day 1).

For programming implementation, a patient is defined as TD if the total RBCs is ≥ 11 units during 26 weeks on or prior to Cycle 1 Day 1.

Non-Transfusion dependent (NTD)

NTD patients are those who do not meet the above definition for TD. For programming implementation, NTD patients are defined as those who received < 11 units of RBCs during 26 weeks on or prior to Cycle 1 Day 1.

Baseline Hemoglobin

Baseline hemoglobin will be an average of hemoglobin measurements within 28 days of Cycle 1 Day 1, excluding measurements within 14 days following RBC transfusion.

Baseline Transfusion Burden

Baseline transfusion burden will be calculated as the total amount of RBC transfusions during the 12 weeks on or prior to Cycle 1 day 1.

Baseline for Other Parameters

Baseline erythropoietin (EPO) is defined as the maximum test value within 28 days of Cycle 1 Day 1. For all other parameters, baseline is defined as the last observation on or prior to Cycle 1 Day 1.

Transfusion Unit Conversion

The transfusion amount measured in unit “mL” will be converted to “units” according to medical review.

End of Treatment (EOT)

Procedures and evaluations for the end of treatment visit should be performed 28 days (± 7 days) after the last dose of ACE-536.

End of Study (EOS)

Procedures and evaluations for the end of study visit should be performed 28 days (± 7 days) after the Day 113/EOT visit (56 days after the last dose of ACE-536).

Combined Dose Groups

Low dose group includes patients on 0.2mg/kg and 0.4 mg/kg dose cohorts. High dose group include patients with dose level 0.6 mg/kg and above. Suitable summaries may be presented by low/high dose as specified.

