9.3.2. Exclusion Criteria

Eligible patients must not meet **any** of the following criteria:

1. Any clinically significant pulmonary (including pulmonary hypertension), cardiovascular, endocrine, neurologic, hepatic, gastrointestinal, infectious, immunological (including clinically significant allo- or auto-immunization), or genitourinary disease considered by the investigator as not adequately controlled prior to Cycle 1 Day 1.
2. Folate deficiency.
3. Symptomatic splenomegaly.
4. Known positive for human immunodeficiency virus (HIV), active infectious hepatitis B (HBV), or active infectious hepatitis C (HCV).
5. Known history of thromboembolic events \geq grade 3 according to the National Cancer Institute-Common Terminology Criteria for Adverse Events (NCI-CTCAE) v.4.0 (current active minor version).
6. Ejection fraction $<$ 50% by echocardiogram, MUGA or cardiac MRI.
7. Uncontrolled hypertension defined as systolic blood pressure (BP) \geq 150 mm Hg or diastolic BP \geq 95 mm Hg.
8. Heart failure class 3 or higher (New York Heart Association, NYHA, [Appendix 1](#)).
9. QTc $>$ 450 msec on screening ECG.
10. Platelet count $<$ 100 $\times 10^9$ /L or $>$ 1,000 $\times 10^9$ /L.
11. Proteinuria \geq Grade 2.
12. Any active infection requiring parenteral antibiotic therapy within 28 days prior to Cycle 1 Day 1 or oral antibiotics within 14 days of Cycle 1 Day 1.
13. Treatment with another investigational drug or device, or approved therapy for investigational use \leq 28 days prior to Cycle 1 Day 1, or if the half-life of the previous investigational product is known, within 5 times the half-life prior to Cycle 1 Day 1, whichever is longer.
14. Transfusion event within 7 days prior to Cycle 1 Day 1.
15. Patients receiving or planning to receive hydroxyurea treatment. Patients must not have had hydroxyurea within 90 days of Cycle 1 Day 1.
16. Splenectomy within 56 days prior to Cycle 1 Day 1.
17. Major surgery (except splenectomy) within 28 days prior to Cycle 1 Day 1. Patients must have completely recovered from any previous surgery prior to Cycle 1 Day 1.
18. Iron chelation therapy initiated within 56 days prior to Cycle 1 Day 1.
19. Cytotoxic agents, systemic corticosteroids, immunosuppressants, or anticoagulant therapy such as warfarin or heparin within 28 days prior to Cycle 1 Day 1 (prophylactic aspirin up to 100 mg/day is permitted).

20. Pregnant or lactating females.

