10.2.2. RBC Transfusions

Concurrent treatment for anemia with blood transfusions is allowed at the discretion of the investigator, for low hemoglobin levels, symptoms associated with anemia (e.g., hemodynamic or pulmonary compromise requiring treatment) or a comorbidity.

For any RBC transfusions received during the study, collect hemoglobin values just prior to transfusion.

Each TD patient in the expansion cohort will have a defined “pre-transfusion hemoglobin threshold” which will be calculated based on transfusion history and will be used for determining when to transfuse during the study. The baseline pre-transfusion hemoglobin threshold will be the mean of all documented pre-transfusion hemoglobin values during the 12 weeks prior to

C1D1. During treatment, if the pre-transfusion hemoglobin value is increased by ≥ 1 g/dL compared to the baseline pre-transfusion hemoglobin threshold for that patient, transfusion should be delayed by a minimum of 7 days and/or the number of units transfused should be reduced by 1 or more RBC units. Patients may be transfused at the investigator's discretion for symptoms related to anemia or other requirements (e.g., infection).

For the first dose of ACE-536, dosing should occur after a minimum of 7 days post-transfusion; subsequent doses should not be given within 24 hours of transfusion or planned transfusion.

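### The SAP's baseline transfusion burden includes Cycle 1 Day 1, so a TD patient transfused after the first dose on that day can count as a primary responder with no change in transfusion need

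*SAP*

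**What the plan says.** A TD patient is a primary responder if transfusion burden falls by at least 20%. The two documents set the comparison periods differently.

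- **Protocol 15.2.2.** Pretreatment: "The interval during the pretreatment period will be defined as the 12 weeks prior to Cycle 1 Day 1". On treatment: "An interval during the treatment plus follow-up period will be defined as any 12-week interval after Cycle 1 Day 1". Read literally, Day 1 is in neither period.
- **SAP 5.1.** Baseline burden is the "total amount of RBC transfusions during the 12 weeks on or prior to Cycle 1 day 1". The 26-week unit count that separates TD from non-transfusion-dependent (NTD) patients includes Day 1 in the same way.
- **SAP 5.7.1.** Response is a 20% or greater "reduction in RBC transfusion burden during any rolling 12-week window on treatment compared to baseline". On where the search begins, the section says "The rolling 12-week window starts on Day 1 and increments by 1 day". On where it stops, it says "The search window ends on last dose day + 56 days or last day of hemoglobin measurement, whichever is earlier".
- **Transfusion before the first dose.** Exclusion 14 in Protocol 9.3.2 reads "Transfusion event within 7 days prior to Cycle 1 Day 1". Protocol 10.2.2 adds "For the first dose of ACE-536, dosing should occur after a minimum of 7 days post-transfusion". The 24-hour separation in that section, which also covers planned transfusions, is stated for later doses only.
- **SAP 5.13** lists two changes from the protocol: the baseline hemoglobin definition and removal of the efficacy-evaluable population. The baseline transfusion window is not among them. Protocol 15.5 says that departures from its analyses will be indicated in the SAP.

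**The concern.** Counting Day 1 as baseline is harmless for laboratory values, because procedures on a dosing day come before the dose. Transfusions differ. Under the 7-day rules, an eligible patient's Day 1 transfusion can only follow the first dose, and nothing in the documents rules one out. The SAP treats this on-treatment transfusion as pretreatment burden.

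The first search window, Day 1-84, still contains it. Response needs only one qualifying window, however, and Day 2-85 leaves it out. Baseline is then one transfusion higher while the comparison window is not, so an unchanged patient can reach the 20% threshold of the primary TD endpoint. The same convention could also move a patient near the 11-unit limit from NTD to TD, and so to a different endpoint.

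**Working it through.** The plan gives no figure for this point. Its one design figure, about 87% power for 30% v 10% with n = 30, does reproduce. The normal approximation with continuity correction has standard errors √(0.1×0.9/30) = 0.0548 and √(0.3×0.7/30) = 0.0837, so power is Φ[(0.20 − 1/60 − 1.645×0.0548)/0.0837] = 86.7%. Nothing below depends on it.

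**Inputs from the documents.** The SAP baseline is 84 days ending on Day 1 (Day -83 to Day 1, with no Day 0). The protocol baseline is Day -84 to Day -1. The search runs from Day 1 to last dose + 56 days, which is Day 85 + 56 = Day 141, giving 141 − 84 + 1 = 58 windows.

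**Assumptions.** Equal units at each transfusion, a fixed interval of T days, one transfusion on Day 1 and no drug effect. The documents give no transfusion interval, so I take T = 14 to 28. At 2 units per transfusion, 28 days is the longest interval that meets the protocol's TD definition (2×56/28 = 4 units per 8 weeks).

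**Counts**, with ⌊x⌋ meaning rounded down:

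- SAP baseline: ⌊83/T⌋ + 1
- Protocol baseline: ⌊84/T⌋
- Window Day 2-85: ⌊84/T⌋, which is also the lowest count in any window
- Reduction = 1 − (lowest window count)/(baseline count)

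| T (days) | SAP baseline | Lowest window | Reduction, SAP | Protocol baseline | Reduction, protocol |
|---|---|---|---|---|---|
| 14 | 6 | 6 | 0% | 6 | 0% |
| 15-16 | 6 | 5 | 16.7% | 5 | 0% |
| 17-20 | 5 | 4 | 20% (responder) | 4 | 0% |
| 21 | 4 | 4 | 0% | 4 | 0% |
| 22-27 | 4 | 3 | 25% (responder) | 3 | 0% |
| 28 | 3 | 3 | 0% | 3 | 0% |

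**Example.** Take 2 units every 24 days, including Day 1. The SAP baseline holds Days -72, -48, -24 and 1, or 8 units. Day 1-84 also holds 8 units (0%). Day 2-85 holds Days 25, 49 and 73, or 6 units, a reduction of 1 − 6/8 = 25%. The protocol baseline is 6 units, so the reduction is 0%.

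**If the SAP window is programmed as 85 days** (Day 1 and the 84 days before it), the baseline is ⌊84/T⌋ + 1. On totals, T = 21 then gives 5 v 4 (20%) and T = 28 gives 4 v 3 (25%), so both respond. T = 14 gives 7 v 6 (14.3%) and does not. The 20% cases rest on comparing totals. Dividing by days, as the protocol's burden ratio does, gives 1 − (4/84)/(5/85) = 19.0%, just short.

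**All permitted timings, not only Day 1.** For each T, I let the first transfusion on or after Day 1 fall on any day that leaves the previous one at least 7 days before Day 1. Over T = 14 to 28 this gives 8 + 9 + … + 22 = 225 timings. False responders:

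- SAP, 84 days: 51 (22.7%)
- SAP, 85 days: 60 (26.7%)
- Protocol baseline: 48 (21.3%)

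At T = 24 the SAP (84 days) and protocol baselines each give 6 of 18. If a transfusion exactly 7 days before is also barred, each gives 5 of 17. Under the 84-day reading the two differ only at T = 20, 26 and 27, by one timing each.

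**TD/NTD count.** A patient with 10 units in the 26 weeks before Day 1 and 2 units after the dose on Day 1 totals 12. That meets the 11-unit rule, so the patient is classed TD.

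**The case against.** The strongest reply is that the fix hardly alters the false-response rate: 51 v 48 of 225 timings under the 84-day reading. Nearly all false responses come from searching 58 windows for the best one, which is a separate problem. This stands. It limits what the fix can achieve, but it does not justify counting a post-dose transfusion as baseline.

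Four stronger readings are tempting, and the documents do not support them.

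- **That the SAP wording always favours the drug.** This is true only of patients transfused on Day 1. An 84-day window that gains Day 1 loses Day -84. With transfusions every 24 days on Days -84, -60, -36, -12 and 13, the protocol baseline is 4 transfusions against a best window of 3 (25%, a responder). The SAP baseline is 3 (0%, not a responder).
- **That longer intervals show a larger effect.** Intervals of 29-41 days would give 3 v 2, or 33%. At 2 units, though, any interval above 28 days averages under 4 units per 8 weeks, below the protocol's TD definition. Those figures would matter mainly for patients given more than 2 units at a time.
- **That Day 1 is a likely transfusion day.** The documents say nothing about how often this happens. The number may be zero.
- **That the overlap of the two periods is itself the cause.** Day 1-84 alone shows no reduction, and starting the search on Day 2 without changing the baseline leaves the result as it is (25% at T = 24). The cause is crediting a post-dose transfusion to baseline.

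It is also fair to say that SAP 5.13 claims to list only major changes, that no hypothesis test is planned, and that every transfusion record will be listed by patient, so any Day 1 case would be visible.

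**Conclusion.** The discrepancy is in the text, and it gives a wrong result for an identifiable kind of patient. A TD patient on an unchanged fixed schedule with a transfusion on Day 1 is a false primary responder at intervals of 17-20 and 22-27 days under an 84-day SAP baseline, and never under the protocol baseline. These figures assume equal units, a fixed interval and no drug effect.

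The effect on the reported response rate cannot be sized, because the number of TD patients transfused on Day 1 is not given. For scale only, one false responder among the 12 TD patients that the expansion cohort must at least contain is 1/12 = 8.3 percentage points. At these intervals the artefact is at most 25%, so alone it does not create a 50% reduction over 12 weeks.

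Severity is minor. The damage is to a descriptive estimate and its interval, in a subset that may be empty.

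**What to change.** In SAP 5.1, define baseline transfusion burden as the RBC units given from Day -84 to Day -1, and end the 26-week TD/NTD count on Day -1. Day 1 transfusions then count only as on-treatment. Naming the days also settles whether the window is 84 or 85 days long.

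List in SAP 5.13 any departure from the protocol that remains. One is that the SAP search starts on Day 1, whereas the protocol's intervals lie after it.

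The cost is a phrase in each definition, the matching program lines and an entry in SAP 5.13. No new data are needed. The change removes only the Day 1 route to a false response. The best-window search needs its own remedy.
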